1 STUDY DETAILS

[figure not shown]
This statistical analysis plan (SAP) for study D5180C00018 outlines the statistical analyses specified in the latest version of the Clinical Study Protocol (CSP) in more detail; any changes to what is specified in the CSP will be described in Section 6.

1.1 Study objectives

For the outcome measures below, "Analysed separately by predecessor study" means that the predecessor study data and LTE study data will be combined but will be analysed separately for subjects originally enrolled in D5180C00007 from those originally enrolled in D5180C00009.

Table 1 Objectives and Endpoints

| Primary objective: | Outcome Measure: |
|--|---|
| To evaluate the long-term safety and tolerability of tezepelumab in severe asthma subjects | Exposure adjusted rates of AEs/SAEs over 104 weeks |
| | Analysed separately by predecessor study |
| Secondary objective: | Outcome Measure: |
| To assess the long-term effect of 210 mg tezepelumab SC Q4W on asthma exacerbations in adult and adolescent subjects with severe | Annualized asthma exacerbation rate (AAER) over 104 weeks (Baseline is week 0 in predecessor study) |
| uncontrolled asthma compared with placebo | Analysed separately by predecessor study |

1.2 Study design

This is a multicentre, randomised, double-blind, placebo controlled, parallel group, phase 3 LTE study designed to evaluate the safety and tolerability of 210 mg Q4W (SC) of tezepelumab in adults and adolescents with severe, uncontrolled asthma on medium to high-dose ICS and at least one additional asthma controller with or without OCS. Subjects who have continued to receive investigational product and have attended the End of Treatment (EOT) visit in one of the predecessor studies, week 52 in study D5180C00007 or week 48 in study D5180C00009, on investigational product (IP) may be eligible to enrol into this study if they fulfil the inclusion/exclusion criteria.

[figure not shown]
The aim of this study is to evaluate the safety and efficacy over 104 weeks. Data from the predecessor studies will be integrated with the data from DESTINATION but will be reported separately for subjects enrolled in D5180C00007 from those enrolled in D5180C0009 unless otherwise stated explicitly.

This study will be run at approximately 350 sites worldwide and will randomise approximately 975 subjects worldwide. All subjects will be re-randomised in this study to maintain the blinding. Subjects previously randomised to the 210 mg tezepelumab Q4W SC arm in either of the predecessor studies, will be assigned to remain on 210 mg tezepelumab Q4W SC dosing in DESTINATION. Subjects randomised to placebo arm in the predecessor studies will be re-randomised in a 1:1 ratio to either 210 mg tezepelumab or placebo, both administered Q4W SC. Given the randomisation scheme of subjects in the predecessor studies, this will give an overall subject distribution of 3:1 (tezepelumab:placebo), assuming a similar number of subjects rollover from each arm in the predecessor studies. See Figure 1 below for the general study design.

Figure 1 Study Design

| Week 0-48 Week 52 V | LONG TERM EXTENDED (LTE) STUDY | | | | | | |
|----------------------------|--------------------------------|------------------------------------|---------------------|-----------|----------|-----|--|
| | Predecessor EOT/V1 | V2 | V3 - V14 | V15 | V16, V17 | CCI | |
| | Week 52 Visit (D5180C00007) | | Week | Week | Week | | |
| Week 0-44 (D5180C00009) | | Week 52 for D5180C00009 only | W | 104 | 110, 116 | | |
| Treatment Phase | Treatment Phase | | End of Treatment | Follow-up | | | |

V: Visits

Subjects who discontinue IP, do not attend the EOT visit in one of the predecessor studies or do not meet the entry requirements for DESTINATION will not be eligible to participate in DESTINATION.

Subjects who are not able to attend an on-site EOT visit in the predecessor study/Visit 1 in the DESTINATION study due to the COVID-19 pandemic, are still allowed to roll-over to the DESTINATION study by the end of the safety follow-up of the predecessor study after confirmation of subject eligibility.

In order to provide sufficient time for subjects to consider participation in this study, and to ensure an uninterrupted dosing regimen, as subjects transition between the predecessor study and DESTINATION, subjects will be provided with the Informed Consent Form (ICF) at/after the visit at which they receive their last dose of IP in the predecessor study and will be asked to sign the ICF at Visit 1 of the LTE study prior to any study-specific procedures being performed.

Section 6.5 of the CSP provides a list of medication restrictions and prohibitions to be followed throughout conduct of the clinical trial.

The study will consist of a screening/randomisation visit which will be the same day as the EOT visit from the predecessor studies D5180C00007 (Week 52) or D5180C00009 (Week 48). The first dose of IP will be administered the same day in most cases unless some delays (for example, due to COVID-19). A treatment period duration of 52 weeks for subjects who previously completed study D5180C00007 or 56 weeks for subjects who previously completed the D5180C00009 will follow. The last dose of IP will be administered at Week 100. EOT visit will be conducted at Week 104. IP will not be administered at Week 104. Subjects that complete the treatment period in DESTINATION will either complete a 12 week follow up period which includes 2 follow-up visits

During the screening/randomisation visit, subjects must undergo all assessments as detailed in Table 1 of the CSP.

Prior to randomisation, the subjects must meet all inclusion/exclusion criteria for DESTINATION. If a subject does not meet all inclusion criteria or meets any exclusion criteria as per section 5.1 and section 5.2 of the CSP, the subject will be screen failed and would then complete the safety follow-up portion of the predecessor study. Further details are specified in the CSP section 5.4.

All subjects who prematurely discontinue IP should return to the study centre and complete the procedures described for the premature IP Discontinuation visit (IPD) at 4 weeks (+/-5 days) post last IP administration. Subjects who prematurely discontinue treatment should be encouraged to return for all regularly scheduled visits for safety and efficacy assessments. At

the IPD visit the subject will be given three options as to how they will be followed (further information is provided in the CSP section 7.1.1):

- 1. Ideally the subject should continue all regular clinic visits and perform all scheduled assessments (excluding IP administration) until the scheduled EOT visit at week 104 (+/-5 days).
- 2. (If the subject cannot comply or does not wish to comply with option 1 above), the subject will be offered follow-up on a monthly basis via telephone calls. The subject should return for an on-site follow up visit 16 weeks (+/- 5 days) (refer to SoA, V17 Week 116) post last IP administration and for the on-site EOT visit at Week 104 (+/-5 days).
- 3. (If the subject cannot or does not wish to comply with option 1 or option 2), they will complete an on-site follow-up visit at 16 weeks (+/-5 days) (refer to SoA, Visit 17 week 116) post last IP administration. After this visit the Investigator will only contact by phone the subject at week 104 (+/-5 days). No other study assessments will be performed prior to this contact.

CCI

During the initial part of the study, subjects, Investigators/site staff and the Sponsor/designated CRO will be blinded to treatment. At the planned unblinding of the predecessor studies D5180C00007 or D5180C00009, the blind for DESTINATION will be maintained for the subjects, Investigators/site staff or any CRO handling data. However, the individual treatment allocation for subjects in DESTINATION may become known to the Sponsor. The Sponsor has designated that there will be 3 separate teams for DESTINATION; an AZ Core Blinded team, AZ Partially blinded team, and an AZ Extended Blinded team (see D5180C00018 Blinding Plan for further details).

To prevent complete unblinding of this study, treatment-revealing information will not be shared with the subjects, Investigators/site staff and CRO, and the AZ Core Blinded study team. The only exception to this is information regarding any deaths reported during the predecessor studies.

2 ANALYSIS SETS

2.1 Definition of analysis sets

For purposes of analysis, the following populations are defined below in Table 2.

Note that subjects included in the SAF and SAF-LTE analysis sets will be assigned to the treatment they are randomised to in the predecessor and LTE studies. In the case of discrepancies between the randomised and actual treatment, where a subject randomised to placebo, receives at least one dose of tezepelumab then all data from the date of the incorrect treatment within that time period (predecessor study, LTE study) will be excluded from the analysis and will be listed separately.

This is a different approach from the reporting of the individual predecessor studies, where treatment is based on the treatment subjects received in the case of any discrepancies between randomised and actual treatment. The reason for the difference in approaches is to avoid adding further complexity to the treatment groups as defined in Section 2.1.2.

Table 2 Analysis sets

| Population | Description |
|---------------------------|--|
| Safety analysis set (SAF) | All subjects who were randomised and received at least 1 dose of IP in any of the predecessor studies, irrespective of their protocol adherence and continued participation in any of the studies, and regardless of their enrolment into this LTE study. Subjects will be assigned according to their randomised treatment. However, if a subject randomised to placebo receives an incorrect treatment, all data after the date the incorrect treatment was received within that time period (predecessor study, LTE study) will be excluded from the analysis, and listed separately. If a subject randomised to tezepelumab receives an incorrect treatment, it will still be regarded as a tezepelumab subject and no data will be excluded after the dose of placebo. Other incorrect dosing, if any, will be handled case-by-case. |

| Population | Description |
|-------------------------|---|
| SAF-LTE | Subjects who were randomised and received at least 1 dose of IP in the LTE study. |
| | Subjects will be assigned according to their randomised treatment. However, if a subject randomised to placebo receives an incorrect treatment, all data after the date the incorrect treatment was received within that time period (predecessor study, LTE study) will be excluded from the analysis, and listed separately. If a subject randomised to tezepelumab receives an incorrect treatment, it will still be regarded as a tezepelumab subject and no data will be excluded after the dose of placebo. Other incorrect dosing, if any, will be handled case-by-case. |
| Full analysis set (FAS) | All subjects who were randomised and received at least 1 dose of IP in any of the predecessor studies, irrespective of their protocol adherence and continued participation in any of the studies, and regardless of their enrolment into this LTE study. |
| | Subjects will be assigned according to their randomised treatment. |
| FAS-LTE | Subjects who were randomised and received at least 1 dose of IP in the LTE study. |
| | Subjects will be assigned according to their randomised treatment. |
| CCI | |
| | |
| | |

The SAF is the primary population for the reporting of the safety data. The FAS is the primary population for the reporting of efficacy data. The SAF-LTE, FAS-LTE will be used for supportive analyses only.

The main summaries of demographics and baseline characteristics will be based on the SAF and SAF-LTE analysis sets, but additional summaries may be provided as detailed in Section 4.2.

In addition to the analysis sets defined above, LTE analysis set will be defined as all subjects who signed the informed consent for the LTE study. This analysis set will be used for reporting the disposition data during the LTE period.

2.1.1 Handling of other issues which may impact analysis sets

[figure not shown]
In a similar manner to the approach taken in the predecessor studies, if it is found that any subject has been randomised on more than one occasion (contrary to the protocol) under different subject numbers, either at the same site or at different sites, then data corresponding to the first subject participation will be used in the analyses. Data associated with the second (and any subsequent) participation of the same subject will be listed and discussed in the CSR. All data associated with duplicate randomisations will be reviewed, and decisions regarding the analysis and reporting of these data will be documented, prior to unblinding at the primary database lock for the predecessor studies and also the LTE study.

The above analysis set definitions assume the integrity of data captured from all participating sites in the trial. If it is deemed necessary to exclude subjects from analysis sets due to suspected fraud/other serious non-compliance at a particular site, or to perform sensitivity analyses with subjects from such a site removed for the same reason, this will be documented in this SAP (amended if necessary) where this is possible prior to database lock. Otherwise, it will be fully described in the CSR. The SAP will not be updated for this after database lock.

2.1.2 Treatment groups

There are 5 possible groupings across the predecessor and LTE studies as shown in Figure 2 below.

Figure 2 Treatment groupings

[figure not shown]

Note: Groups 2 and 5 reflect subjects in the predecessor studies who do not enrol in the LTE study.

The following treatment groups for analyses will be considered, where time from first dose is applicable for the safety analysis, and time from randomisation is applicable for the efficacy analysis:

Primary (based on the SAF and FAS analysis sets):

[figure not shown]
- Randomised Tezepelumab (Rand Teze): All subjects originally randomised to tezepelumab in the predecessor studies. Will include all data from first dose/randomisation in the predecessor studies to end of the LTE study. (A, B and C)
- Randomised Placebo (Rand Pbo): All subjects originally randomised to placebo in the predecessor studies. Will include all data from first dose/randomisation in predecessor studies up until switch to tezepelumab, and all data from first dose/randomisation in the predecessor studies to end of the LTE study for subjects randomised to placebo in the predecessor studies and the LTE study. (D, F, G and H)

Supportive (based on the SAF-LTE and FAS-LTE analysis sets):

[figure not shown]
- Tezepelumab Predecessor+Tezepelumab LTE (Teze+Teze): All subjects originally randomised to tezepelumab in the predecessor studies and re-randomised to tezepelumab in the LTE study. Will include all data from first dose/randomisation in the predecessor study to end of the LTE study for only subjects enrolled into the LTE study. (A and B)
- Placebo Predecessor+Placebo LTE (Pbo+Pbo): All subjects randomised to placebo in the predecessor studies, and later re-randomised to placebo in the LTE study. Will

include all data from first dose in predecessor studies until end of the LTE study for only subjects enrolled into the LTE study. (F and G)

[figure not shown]
Supportive (for exposure summaries and rare events based on the SAF analysis set):

[figure not shown]
• All Tezepelumab (All Teze): All subjects randomised to tezepelumab in the predecessor studies and subjects randomised to tezepelumab in the LTE study. It will include all data from time of first dose/randomisation to tezepelumab. (A, B, C and E)

Additional (for the assessment of durability of benefit based on the SAF-LTE and FAS-LTE analysis sets):

- Tezepelumab Predecessor+Tezepelumab LTE (Teze+Teze): as defined above
- Placebo Predecessor+Placebo LTE (Pbo+Pbo): as defined above
- Placebo Predecessor+Tezepelumab LTE (Pbo+Teze): All subjects originally randomised to placebo in the predecessor studies and re-randomised to tezepelumab in the LTE study. Will include all data from first dose/randomisation in the predecessor studies to end of the LTE study for only subjects enrolled into the LTE study. (D and E)

2.2 Violations and deviations

Important protocol deviations (PDs) will be listed and tabulated in the Clinical Study Report (CSR) only for randomised subjects. These are defined as PDs which may significantly affect the completeness, accuracy and/or reliability of the study data, or which may significantly affect a subject's rights, safety, or well-being. Important PDs in this study will be grouped under one of the following categories (refer to Protocol Deviation Plan):

- Did not fulfil key eligibility criteria
- Developed discontinuation criteria during the LTE study but continued IP
- Received prohibited concomitant medication during the LTE study

- Did not comply with restrictions during the study
- IP management issues

All important PDs, except Code 10.9 receiving wrong IP kit number and Code 10.22 IP dose in excess of 700 mg administered within a 2-week period, will be identified and documented by the study team prior to unblinding of the LTE study. As far as possible, the occurrence of important PDs will be monitored (blinded) during the study, with the emphasis on their future prevention.

The study PD Plan outlines the management of PDs and includes the proposed specific categories of PDs in this study. Any PDs which are not defined as important or COVID-19 related will not be reported and discussed in the CSR.

3 PRIMARY AND SECONDARY VARIABLES

For the definition of primary and secondary variables, unless stated otherwise, all references to Day 1 and date of first dose of IP, refer to the respective day in the predecessor studies. The date of last dose of IP refers to the last dose during the LTE study for subjects who enrol in the LTE study (and received IP in the LTE study) and the last dose of IP in the predecessor studies for subjects not continuing into the LTE study.

3.1.1 Data integration

Data from the predecessor studies will be integrated with the data from the LTE study. However, data will be reported separately for subjects initially enrolled in D5180C00007 from those initially in enrolled in D5180C00009, unless otherwise stated.

Subjects are assigned new enrolment codes (ecodes) in the LTE study from those assigned in the predecessor studies. The new ecodes will not overlap with those used in the predecessor studies. The SUTRA eCRF module in the database for the LTE study provides the decode link to allow subjects data across the studies to be integrated.

Ongoing AEs, concomitant medications and exacerbations will be recorded in both the predecessor study database and the LTE study database. If possible, they will be combined into one record for the purpose of analysis, based on the worst case (e.g., an ongoing AE recorded as mild in the predecessor study and recorded as moderate in the LTE study will be reported as one AE of moderate intensity).

Throughout this document reference to a particular week is in relation to Week 0 from the predecessor study (e.g., for study D5180C00007, Week 12 refers to 12 weeks after randomisation in the predecessor study; Week 64 refers to 12 weeks after enrolment into the LTE study).

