### **8.3.4 Adverse event data collection**

The following variables will be collected for each AE:

- AE (verbatim)
- The date when the AE started and stopped
- Whether the AE is serious or not
- Investigator causality rating against the Investigational Product(s) (yes or no)
- Action taken with regard to Investigational Product(s)
- AE intensity (mild, moderate, severe)
- Outcome.

In addition, the following variables will be collected for SAEs:

- Date AE met criteria for serious AE

Tezepelumab - D5180C00018

- Date Investigator became aware of serious AE
- AE is serious due to
- Date of hospitalisation
- Date of discharge
- Probable cause of death
- Date of death
- Autopsy performed
- Causality assessment in relation to Study procedure(s)
- Causality assessment to other medication(s)

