## **Appendix B Adverse event definitions and additional safety information**

### **B 1 Definition of adverse events**

An adverse event is the development of any untoward medical occurrence in a subject or clinical study subject administered a medicinal product and which does not necessarily have a causal relationship with this treatment. An AE can therefore be any unfavorable and unintended sign (e.g. an abnormal laboratory finding), symptom (for example nausea, chest pain), or disease temporally associated with the use of a medicinal product, whether or not considered related to the medicinal product.

The term AE is used to include both serious and non-serious AEs and can include a deterioration of a pre-existing medical occurrence. An AE may occur at any time, including run-in or washout periods, even if no Study treatment has been administered.

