3.2.2 Adverse events – general

Adverse events (AEs) experienced by any subject at any time during the entire study will be coded using the latest version of the Medical Dictionary for Regulatory Activities (MedDRA) at the time of the primary database lock. This version of MedDRA will also be used during the final database lock.

AEs will be categorised for analysis according to their onset date into the following study periods for the SAF and SAF-LTE analysis sets:

- AEs occurring during screening/run-in period: date of Visit 1 in the predecessor study ≤
 AE onset date < date of first dose of IP in the predecessor study
- AEs occurring during on-treatment period: date of first dose of IP \leq AE onset date \leq minimum (date of last dose of IP + 33 days, date of death, date of study withdrawal)
- AEs occurring during post-treatment/follow-up period (for subjects still being followed up then): date of last dose of IP + 33 days < AE onset date ≤ study completion or withdrawal date
- AEs occurring during on-study period: date of first dose of IP ≤ AE onset date ≤ study completion or withdrawal date.

In addition, AEs will be further categorised for analysis for the on-treatment and on-study periods by the predecessor and LTE time periods as defined in Section 3.1.5.1.

If the AE has a completely missing (and unresolvable) onset date, then the AE will be assumed to have occurred during the on-treatment period, unless the end date indicates unambiguously that the AE resolved before treatment started. If the AE has a partially missing (and unresolvable) onset date, then the AE will also be assumed to have occurred during the on-treatment period, unless either the end date indicates unambiguously that the AE resolved before treatment started, or the partial onset date is in the month/year prior to start of treatment.

For each treatment group, exposure adjusted incidence rates will be defined as the number of subjects reporting adverse events divided by total exposure duration for that treatment group.

For individual subjects, exposure duration (days) for each time period is derived using the start date and end date defined for the on-treatment and on-study period in Section 3.1.5.1. The total exposure duration (years) for a treatment group will be derived as the sum of the individual subject exposure duration (days) for that treatment group and divided by 365.25.

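### For subjects who switch from placebo to tezepelumab, the worst-case merge of ongoing AEs reports post-switch worsening under placebo

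*SAP*

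**What the plan says.** - **Merging.** Under SAP 3.1.1, AEs ongoing at roll-over are recorded in both the predecessor and the LTE database. "If possible, they will be combined into one record for the purpose of analysis, based on the worst case". The example concerns intensity: "an ongoing AE recorded as mild in the predecessor study and recorded as moderate in the LTE study will be reported as one AE", and that one AE is moderate.
- **Placement.** SAP 3.2.2 states that "AEs will be categorised for analysis according to their onset date". A second rule refines this: "AEs will be further categorised for analysis for the on-treatment and on-study periods by the predecessor and LTE time periods". The date of worsening, of becoming serious or of stopping IP plays no part.
- **Treatment groups.** For Randomised Placebo, SAP 2.1.2 says of the subjects who switch: "Will include all data from first dose/randomisation in predecessor studies up until switch to tezepelumab". All Tezepelumab begins at the first tezepelumab dose. Randomised Tezepelumab contains only subjects first randomised to tezepelumab.
- **Outcome.** SAE rates are part of the primary outcome (SAP 1.1). SAP 4.5.1 adds summaries of fatal AEs, DAEs, causality, maximum intensity and each AESI category.
- **Data collected.** Protocol 8.3.4 records one intensity for each AE, with no date of change. For SAEs it also records "Date AE met criteria for serious AE".

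**The concern.** For a subject who stays on the same treatment, combining two records of one event is harmless: whichever period supplies the worst attribute, the treatment is the same. For a subject who moves from placebo to tezepelumab, the merged record can join a placebo onset to a severity reached on tezepelumab. The onset date then decides which treatment carries it.

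The primary objective is long-term safety, and Randomised Placebo is the primary comparator. The summaries exposed to the error include small-count categories, where a few subjects matter. The direction is fixed. Worsening after the switch moves to placebo. An AE that improves after the switch keeps its worse placebo status, which is correct for placebo. Nothing moves the other way.

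**Working it through.** The documents state no figure for this effect, so the check is first a trace of the rules and then an illustration of scale.

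**Trace**

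1. An AE ongoing at roll-over began, by definition, before the first LTE dose. The SAP does not state the onset date of the merged record, but it can only be a predecessor date.
2. By SAP 3.2.2 the merged record falls in the predecessor period.
3. For a switcher, that period is the placebo segment (D in SAP Figure 2), which belongs to Randomised Placebo and to the predecessor column of Placebo Predecessor+Tezepelumab LTE.
4. The onset precedes the first tezepelumab dose, so the record is outside All Tezepelumab and outside the switchers' LTE column.

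Invented example: onset on placebo 20 Dec 2019, mild and non-serious; switch 10 Jan 2020; then severe, serious and leading to IP discontinuation on tezepelumab.

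| Summary | Where the merged record counts |
|---|---|
| Any AE | Placebo, correctly: it began there |
| Maximum intensity | Placebo, as severe |
| SAE and DAE, if the worst case covers all attributes | Placebo |
| Switchers' LTE column; All Tezepelumab | Not counted |

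SAP 4.5.1 plans no intensity or causality table for All Tezepelumab. The loss from that group therefore concerns SAEs, DAEs and AESIs. Severe infection is the clearest AESI, because SAP 8.1.6 defines it partly by seriousness, treatment and discontinuation.

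**Comparison within the SAP.** The switch is handled explicitly for concomitant medications (footnote to 3.1.7), time to last dose (3.1.9), exposure (3.2.1) and exacerbation time at risk (3.3.1.1). The AE merge has no such rule. Placebo exposure is calculated from placebo doses only, while the placebo numerator can carry later attributes.

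**Scale**

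Inputs from the documents: 860 + 115 = 975 subjects entering the LTE; 1:1 re-randomisation of placebo subjects; 3:1 overall; 90% completing the predecessor study and 90% of those continuing. A 1:1 predecessor allocation reproduces the stated ratio: (0.5 + 0.25) : 0.25 = 3:1.

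- Switchers: 975/4 = 243.75, about 244 (860/4 = 215 from D5180C00007; 115/4 = 28.75, about 29, from D5180C00009).
- Predecessor placebo subjects: 975/(0.9 × 0.9)/2 = 602.
- Placebo subject-years, taking 52 weeks for each part and dropouts contributing half: 602 × 0.95 × 52/52.18 = 570, plus 243.75 × 52/52.18 = 243, giving 813 with full LTE completion. With 90% LTE completion the second term is 243 × 0.95 = 231, giving 801.

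The assumed share q of switchers has an AE ongoing at the switch that worsens on tezepelumab in an attribute the merge carries back:

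| q | Subjects misassigned (243.75 × q) | Added to placebo, per 100 subject-years |
|---|---|---|
| 0.5% | 1.2 | 0.15 |
| 1% | 2.4 | 0.3 |
| 2% | 4.9 | 0.6 |
| 5% | 12.2 | 1.5 |

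Results are presented by predecessor study. The same range of q gives 1.1 to 10.8 subjects in D5180C00007 and 0.1 to 1.4 in D5180C00009.

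**The case against.** The best counter-argument is that SAP 3.1.1 names only intensity, hedges with a condition, and can be read subject to 2.1.2, which stops placebo data at the switch. On that reading nothing post-switch reaches the placebo tables. This stands in part: that seriousness, action taken, causality and outcome carry over is an inference from general wording. But the example given is enough to misassign intensity, and nothing tells the programmer that 2.1.2 overrides the merge. The hedge gives little protection, since an unmerged LTE record bearing the true onset date would also be placed in the predecessor period.

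A site may also enter a deterioration as a new AE. Protocol Appendix B 1 says an AE "can include a deterioration of a pre-existing medical occurrence". A new record would have its own onset and fall under tezepelumab. This is real mitigation, but nothing requires it at the switch. A reader might infer that the merge contradicts Appendix B 1. It does not, because that wording is permissive.

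A reader might also infer that the harm disappears from every tezepelumab group, the primary one included. The documents do not support that. Randomised Tezepelumab never contains switchers' LTE data under any rule, so the primary contrast is affected only through the placebo side. Tezepelumab Predecessor+Tezepelumab LTE versus Placebo Predecessor+Placebo LTE, planned overall and by period, crosses no treatment change and is a clean check. A spurious placebo DAE would also clash with the predecessor disposition table, because roll-over subjects must not have discontinued IP early. That clash would not expose a shift in intensity or seriousness.

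Finally, a reader might infer a large distortion of DAEs. Using the Phase 2b placebo figure of 0.7% (one subject, Protocol 2.2) as a yearly risk, the predecessor placebo year gives 602 × 0.7% = 4.2, and the LTE year of about 244 subjects remaining on placebo adds 1.7, for a total of 5.9. Two misassigned DAEs would add 2/5.9, about a third. Judging them against the predecessor year alone would suggest about a half, which is too high. Nothing in the documents says that two would occur.

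**Conclusion.** The point holds as an unreconciled conflict between SAP 3.1.1 with 3.2.2 on one side and 2.1.2 on the other, confined to Placebo Predecessor+Tezepelumab LTE subjects. As written, the rules misassign intensity. If the worst case is applied generally, they also misassign SAE, DAE, fatal, causality and severe-infection summaries. The bias can only favour tezepelumab.

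Its size is not derivable from the documents. The range of about 1 to 12 subjects, or 0.15 to 1.5 per 100 placebo subject-years, rests on an assumed 0.5% to 5% of about 244 switchers, on the planned enrolment, and on similar roll-over from each arm. It is a scale, not an estimate. No hypothesis is tested, so the consequence is for description and interpretation of the safety tables. That is sufficient reason to settle the rule before primary database lock.

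**What to change.** In SAP 3.1.1:

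1. Restrict the worst-case merge to subjects whose treatment is unchanged at LTE entry.
2. For Placebo Predecessor+Tezepelumab LTE subjects, use only the predecessor-database attributes up to the first LTE dose in Randomised Placebo and in predecessor-period tables.
3. List or tabulate separately, for these subjects' LTE period and for All Tezepelumab, each AE ongoing at the switch whose LTE record shows higher intensity, new seriousness, new causality, IP discontinuation or a fatal outcome. Use the date seriousness was met where recorded. Do not impute an onset date for intensity changes.

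It is tempting to go further and count the worsening as a new LTE-period AE in the main tables. That would often require an invented onset, because no date of intensity change is collected, and setting it to the first LTE dose would place the worsening at the start of tezepelumab. It would also split records for switchers only, giving them LTE-period AEs that subjects in the other groups with the same worsening would not receive. A separate display avoids both problems.

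The cost is a short SAP amendment, one programming rule and one extra table or listing. A few AEs will be shown under both treatments for switchers, which a footnote can explain.
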